9.2 Statistical Methods

9.2.1 Concentrations of Abaloparatide-sMTS

Individual concentration of abaloparatide-sMTS will be listed and summarized in accordance with the grouping factors (i.e., day).

Each data subset will be listed by subject and summarized for each nominal time point with the following descriptive statistics: sample size (n), mean (Mean), standard deviation (SD), coefficient of variation (CV%), median (Median), minimum (Min), maximum (Max), geometric mean (Geo Mean) and coefficient of variation of Geo Mean (Geo Mean CV%).

Individual concentrations of abaloparatide-sMTS will be reported at the level of significance presented in the observed data files. Reporting rules for the concentrations and summary statistics, will be as follows:

- Mean: 1 more level decimal/significant digit than the individual value
- Geo Mean: 1 more decimal/significant digit than the individual value
- SD: 1 more decimal/significant digit than the mean
- CV%: always 1 decimal
- Median, Min, Max: same number of decimals/significant digits reported for the individual value.

Individual concentrations will be plotted vs. actual sampling time on linear-linear and log-linear scales (one plot per subject, as appropriate). Mean concentrations (+SD) will be plotted vs. nominal sampling time on linear-linear and log-linear scales using the appropriate grouping factors (day). Additionally, spaghetti plots of abaloparatide-sMTS plasma concentrations will be prepared for each day.

9.2.2 PK Parameters of Abaloparatide-sMTS

Individual plasma PK parameters of abaloparatide-sMTS will be listed and summarized in accordance with the grouping factors (i.e., day). PK parameters will be summarized with the following descriptive statistics: n, Mean, SD, CV%, Median, Min, Max, Geo Mean and Geo Mean CV%.

Reporting rules for the PK (with the exception of C_{max}) and summary statistics will be as follows:

- Individual values with the number of decimals/significant digits that will allow at least 3 significant figures to be presented for the minimum value of the parameter, except for t_{max} which are parameters of time to be reported with 2 decimals.
- N: integer
- Mean: 1 more decimal/significant digit than the individual value
- Geo Mean: 1 more decimal/significant digit than the individual value
- SD: 1 more decimal/significant digit than the mean
- CV% of Geo Mean CV%: always 1 decimal
- Median, Min, Max: same number of decimals/significant digits as the individual value

Individual and summary statistics for the PK parameter C_{max} will follow the reporting rules described for concentrations of abaloparatide-sMTS ([Section 9.2.1](#)).

9.2.3 Statistical Analysis

Comparisons between the abaloparatide PK parameter values on Day 15 and on Day 29 vs Day 1 will be conducted. Variable identifying the day (e.g., PKDAY or VISIT) will be used as fixed effect.

The log transformed AUC0-t, AUC0-inf, and Cmax will be compared among the visits following the methodology of the longitudinal data analysis using a repeated measures model. SAS® Proc MIXED will be used to account for the possibility of having the unbalanced data. Model will have no random effects, however, since the repeated observations for the same subject made on several days will be used in the model, several forms of variance covariance matrices will be explored, e.g., compound symmetry (CS), the first- or nth-order autoregressive covariance matrices, [AR(1) and TOEP respectively], and unstructured (UN) form. The one that produces the minimal corrected Akaike information criterion (AICC) will be used in the final model. Point estimates and 90% CIs for treatment differences on the log scale, obtained from the model, will be exponentiated to obtain estimates on original scale.

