#### 8.4.2. Analysis of the Primary Endpoint

The primary population for the analysis of the PK parameters will be the PK Analysis Population.

Individual plasma concentrations of abaloparatide will be listed and summarized by visit and sampling time. Concentration data will be summarized at each nominal time point with the following descriptive statistics: number of subjects, mean, SD, coefficient of variation (CV%), median, minimum, and maximum. Individual plasma concentrations will be plotted vs nominal sampling time on linear-linear and log-linear scales by visit. Spaghetti plots of abaloparatide plasma concentrations will also be prepared.

Parameters	Description
AUC 0-t	Area under the plasma concentration-time curve from time zero to the time of the last quantifiable concentration
AUC 0-inf	Area under the plasma concentration-time curve from time zero to infinity
$C_{max}$	Maximum observed plasma concentration
t max	Time of maximum observed plasma concentration
t 1/2	Apparent terminal phase half-life
$\lambda_z$	Elimination rate constant

All plasma PK parameter calculations will be performed using actual time (or nominal time, when actual time is not available) calculated relative to the time of study drug administration. PK parameters will be determined using non-compartmental methods based on individual plasma concentration-time data for abaloparatide. Individual plasma PK parameters will be listed and summarized by visit. PK parameters will be summarized with the following descriptive statistics: number of subjects, mean, SD, CV%, median, minimum, maximum, geometric mean (Geo Mean), and coefficient of variation of the geometric mean (Geo Mean CV%).

Comparisons between the abaloparatide PK parameter values on Day 15 and on Day 29 vs Day 1 (based on natural log (ln)-transformed  $AUC_{0-inf}$ ,  $AUC_{0-t}$ , and  $C_{max}$ ) will be conducted. Point estimates and 90% CIs for the difference in PK parameter values between visits will be obtained. Further details will be described in the Pharmacometric Analysis Plan.

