7.3 Number of Subjects

Approximately 22 subjects will be enrolled and treated to ensure a minimum of 18 subjects complete the 29-day treatment and study procedures.

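### Choosing the primary PK covariance structure by minimum AICC can leave the 90% CI for Day 15 vs Day 1 with about 85–87% coverage if Day 1 is the less-correlated day

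*SAP*

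**What the plan says.** The primary endpoint is systemic exposure on Days 1, 15 and 29 (Protocol 2.2). Protocol 8.4.2 promises interval estimates: "Point estimates and 90% CIs for the difference in PK parameter values between visits will be obtained". The model is left to the PAP, which is bound with the SAP.

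PAP 9.2.3 sets the contrasts: "Comparisons between the abaloparatide PK parameter values on Day 15 and on Day 29 vs Day 1 will be conducted". On the mean structure it says "Variable identifying the day (e.g., PKDAY or VISIT) will be used as fixed effect", and then "Model will have no random effects". Within-subject dependence is carried by a covariance matrix, for which several forms will be "explored, e.g., compound symmetry (CS), the first- or nth-order autoregressive covariance matrices, [AR(1) and TOEP respectively], and unstructured (UN) form". The list opens with e.g., so it is not closed. The choice among them is mechanical: "The one that produces the minimal corrected Akaike information criterion (AICC) will be used in the final model". The results are then back-transformed: "Point estimates and 90% CIs for treatment differences on the log scale, obtained from the model, will be exponentiated".

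Neither PAP 9.2.3 nor PAP 9.4 (software) names a degrees-of-freedom method, a small-sample adjustment, a robust variance or a sensitivity analysis under a fixed structure. On size, PAP 7.3 states: "Approximately 22 subjects will be enrolled and treated to ensure a minimum of 18 subjects complete the 29-day treatment and study procedures".

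**The concern.** Every planned contrast uses Day 1, so its standard error depends on how the model describes Day 1's variance and Day 1's correlations with the later days. CS, AR(1) and TOEP share one variance across days. CS makes all correlations equal. AR(1) and TOEP make the Day 1–Day 15 correlation equal to the Day 15–Day 29 correlation. None of the three can describe a Day 1 that sits apart from two similar later days.

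That pattern is plausible. Day 1 is the first self-application, straight after training, while Days 15 and 29 follow two and four weeks of daily use. UN can describe it, but AICC charges UN for six covariance parameters against two for CS or AR(1). When a simpler form wins, the data are pooled in a way that overstates the Day 1–Day 15 correlation, and the interval comes out too narrow. These CIs are the only interval estimates planned for the primary endpoint, and a reader would use them to judge whether exposure is maintained under self-administration.

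**Working it through.** **Inputs.** From the documents: three days, day as the only fixed effect, no random effects, the four named structures, minimum AICC, 90% intervals (PAP 9.2.3), and 18 to 22 subjects (PAP 7.3). Assumed because the documents are silent: the SDs and correlations (varied over a range), complete data, log-normality, REML, and SAS default degrees of freedom of 2(n−1) for CS, AR(1) and TOEP and n−1 for UN. The documents state no coverage, variance or power figure, so there is nothing to reproduce first.

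**Step 1: how hard AICC makes it to choose UN.** The penalty is 2d·n*/(n*−d−1), with d covariance parameters and n* = 3n−3.
- n = 18, n* = 51: d = 2 gives 204/48 = 4.25; d = 6 gives 612/44 = 13.91; difference 9.66.
- n = 22, n* = 63: d = 2 gives 252/60 = 4.20; d = 6 gives 756/56 = 13.50; difference 9.30.

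UN must therefore lower −2 log-likelihood by more than 9 relative to CS or AR(1) before it is selected.

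**Step 2: what the simpler forms do to the standard error.** Take equal SDs (set to 1) and correlations 0.5 (Days 1–15), 0.5 (Days 1–29) and 0.8 (Days 15–29). The true variance of either Day 1 difference is 2(1−0.5) = 1.0 per subject.
- CS pools to (0.5+0.5+0.8)/3 = 0.6. Modelled variance is 2(1−0.6) = 0.8, so the SE ratio is √0.8 = 0.89 for both contrasts.
- AR(1) settles at the mean lag-one correlation, (0.5+0.8)/2 = 0.65. For Day 15 the modelled variance is 2(1−0.65) = 0.70, SE ratio 0.84. For Day 29 the modelled correlation is 0.65² = 0.4225, variance 2(1−0.4225) = 1.155, SE ratio 1.07.

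Day 15 is thus understated under both forms. Day 29 is understated under CS and overstated under AR(1), and these largely cancel.

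**Step 3: coverage of the whole procedure.** In each simulated trial all four structures were fitted and the minimum-AICC one supplied the interval (20,000 trials per row; Monte Carlo SE about 0.25 points).

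| Assumed truth (correlations 1–15 / 1–29 / 15–29) | n | UN chosen | Day 15 vs Day 1 | Day 29 vs Day 1 |
|---|---|---|---|---|
| CS, all 0.5 | 18 | 4% | 89.7% | 90.0% |
| | 22 | 5% | 89.6% | 89.7% |
| 0.5/0.5/0.8, equal SDs | 18 | 28% | 85.7% | 89.4% |
| | 22 | 37% | 86.2% | 89.6% |
| 0.3/0.3/0.6, equal SDs | 18 | 12% | 86.5% | 89.3% |
| | 22 | 16% | 86.7% | 89.3% |
| 0.5/0.5/0.8, Day 1 SD 1.25x | 18 | 50% | 86.6% | 89.4% |
| | 22 | 63% | 87.2% | 89.5% |
| All 0.5, Day 1 SD 1.5x | 18 | 39% | 88.3% | 89.0% |
| | 22 | 51% | 88.7% | 89.4% |

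Fixed UN covered 89–91% throughout. Separate runs at 0.4/0.4/0.7 and 0.5/0.5/0.75 gave 85–87% for Day 15. A Day 1 SD of 2x gave 89–90%, because UN is then chosen 80–99% of the time. A smaller Day 1 SD with equal correlations gave 90–91%. Using n−1 degrees of freedom throughout raised coverage by only 0.3 to 1 point.

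**Step 4: width.** At 0.4/0.4/0.7 and n = 18 the mean log-scale half-width for Day 15 was 0.157 under AICC selection and 0.175 under UN: 0.157/0.175 = 0.90, about 10% too narrow. For a ratio of 1, that is 0.85 to 1.17 instead of 0.84 to 1.19.

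**The case against.** Several points on the other side stand.

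- Minimum AICC is a pre-specified, objective rule, and UN is a candidate. The open list could also admit heterogeneous-variance forms, which were not simulated.
- The triggering correlations are assumed. The design also weakens the learning argument: subjects are trained immediately before the first dose, show that they can apply the patch with the investigator present (Protocol 5.3), and all on-site dosing is supervised (Protocol 5.6). All three PK profiles therefore come from supervised applications after training.
- The end-of-treatment contrast, Day 29 vs Day 1, is nearly unaffected.
- With complete data every structure gives the same point estimate. The study is described as hypothesis generating (Protocol 8.5), has no formal tests (Protocol 8.2) and sets no acceptance limits for these intervals.

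These points limit the consequence. They do not show that the interval has its stated confidence, and the plan offers no fixed-structure analysis to check it against.

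A reader might infer that all the reported CIs cover far below 90%, or that any peculiarity of Day 1 is enough to cause this. Neither is supported. The shortfall is about 3–5 points, falls on one contrast, and needs a lower Day 1 correlation; a variance difference alone costs at most about 1–2 points. Coverage of roughly 79–83% does appear for Day 15 in the two 0.5/0.5/0.8 patterns, but only among trials in which an equal-variance form was selected. It is not the coverage of the procedure.

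**Conclusion.** The concern holds in limited form. If Day 1 is less correlated with Days 15 and 29 than those days are with each other, the nominal 90% CI for Day 15 vs Day 1 covers about 85–87% at 18 to 22 subjects and is about 10% too narrow. Day 29 vs Day 1 stays within about 1–2 points of nominal, and under true compound symmetry there is no loss. No decision rule in the documents changes; what changes is how precisely one primary contrast appears to be known.

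The result rests on assumed correlations, complete log-normal data and SAS default degrees of freedom. Fewer usable profiles would make it somewhat worse. AUC0-inf is the likeliest case, since PAP 9.1.2 withholds it when the terminal fit is poor. If n fell to 12 (an assumption), the lowest Day 15 coverage was about 84–85%.

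**What to change.** In PAP 9.2.3, pre-specify TYPE=UN with Kenward-Roger degrees of freedom for log AUC0-t, AUC0-inf and Cmax, and keep the AICC-selected structure as a sensitivity analysis. With complete data this equals the paired t interval, so under normality its coverage does not depend on the covariance pattern. Six covariance parameters over three visits are estimable with 18 to 22 subjects. The change also closes the open candidate list and stops the three parameters from ending up with different structures.

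If UN does not converge, use paired differences from Day 1 with a paired t interval. CS with an uncorrected sandwich variance is a poorer fallback: with complete data it covered 88.1–88.5% on 2(n−1) degrees of freedom and about 89% on n−1.

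The cost is PAP wording, plus an interval about 3% wider for Day 15 vs Day 1 if compound symmetry truly holds. That matches the ratio of t quantiles at n = 18: 1.740 on 17 degrees of freedom over 1.691 on 34 is 1.03. The simulated cost for Day 29 was about nil. Kenward-Roger with unbalanced data was not simulated; the figures above are for complete data with n−1 degrees of freedom.

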9.3 Data Handling

9.3.1 Handling of Missing Plasma Concentrations

For the PK parameter calculations, missing data may be imputed for:

- Missing pre-dose values: for single dose PK profile (i.e., Day 1), the pre-dose concentration will be set to 0. For steady state, the pre-dose will correspond to the minimum concentration observed during the dose interval.

No imputation will be performed for missing post-dose plasma concentrations. Unless otherwise noted, data summaries will be performed only on observed data.

9.3.2 Time Deviation

If the actual time of blood collection post-dose deviates by >20% from the nominal time, those sample concentrations will be reported (flagged with code “/t”) and included in the PK analysis. They will be excluded from the summary statistics in concentration tables and mean figures.

9.3.3 Incomplete Dosing Information

Missing dose dates and/or times may be imputed using nominal dosing times. The imputation strategy will be discussed with Radius. All pharmacokinetic samples associated to a missing dosing date and/or time that cannot be imputed will be excluded from the analysis.

Subjects with a documented patch adherence issue will be reviewed by CSC and Radius for inclusion/exclusion from the descriptive statistics on a case-by-case basis.

In the case where subjects were dosed with abaloparatide-sMTS but discontinued from the study (early termination), the concentration data will be reported in the concentration tables and included in all summary statistics and PK analysis if sufficient concentration data are available to usefully contribute to the PK analysis.

9.3.4 Missing Sampling Dates and/or Times

Missing sample dates and/or times may be imputed using nominal collection times. The imputation strategy will be discussed with Radius.

9.3.5 Unexpected Data

After database lock, a visual inspection of concentration-time profiles will be performed to determine dataset integrity and potential outliers. Descriptive statistics of PK parameters may be calculated with and without subjects with potential outlier data. Subjects with potential outlier data will be reviewed by CSC and Radius for inclusion/exclusion from the descriptive statistics on a case-by-case basis.

Single-dose PK profiles (i.e., Day 1) with non-zero pre-dose concentration values will be included in the computation of PK parameters and descriptive statistics on PK parameters and concentrations if the value is not greater than 5% of C_{max} . PK profiles with non-zero pre-dose concentration values greater than 5% of C_{max} will be identified in the PK report and will be reviewed by CSC and Radius for inclusion/exclusion from the PK calculations and descriptive statistics on concentrations and PK parameters.

Multiple observations at the same actual time point will be averaged for the calculation of PK parameters.

Any plasma concentrations that cannot be uniquely and unequivocally attributed to a particular subject, dose, or day and/or time point based on case report form (CRF) records or other observed

data records in the study will be treated as incomplete data. Such data will be compiled, commented, and listed separately in the appendix of the report. Incomplete and/or non-compliant data, if any, will be excluded from analysis datasets; no analyses, summaries or graphs will be produced using these data.

9.4 Software

PK parameters of plasma abaloparatide-sMTS will be calculated using a validated version of Phoenix™ WinNonlin® 7.0 or later. Summary tables and figures of abaloparatide-sMTS in plasma will be generated using a validated version of Phoenix™ WinNonlin® 7.0 or later or R Version 3.3.3 or later.

Statistical analysis for the comparisons between the abaloparatide PK parameter values will be performed using SAS® version 9.3 or later.

9.5 Quality Control and Quality Analysis

Data sets, PK analyses, statistical analyses, tables, figures and listings and the report will be 100% quality-controlled (QC'd) by two scientists at CSC (i.e., by the originator of the work and by a reviewer) as per CSC SOP-104 entitled, “Managing Data in CSC” and CSC SOP-114 entitled, “Analysis Workflow in CSC”.

The QC of datasets will involve dataset reconstruction using an appropriate software. This may include the verification of BLQ rules application, management of missing sampling times or concentration data, calculation of actual sampling time points and time deviations, and treatment, cohort and/or dose attribution. Assignments of concentrations to the appropriate dose administration periods (e.g., pre-doses or following dose escalations/de-escalations) will also be reviewed. Datasets and assumptions from the reviewer and authenticator will be compared. The QC of the NCA analysis will include but is not limited to the following items: model settings (use of appropriate post-dose time, PK parameters, units, doses, area under the curve calculation method, etc.), selected time points used for the assessments of λ_z , subject exclusions due to deviation, and the management of missing PK parameters. The QC of the raw outputs (i.e., tables, figures, and listings) will include but is not limited to the following items: the precision of individual values and summary statistics, the comparison of 5 to 10% of values against the raw data, the use of appropriate and consistent abbreviations, axis labels, and footnotes, and the presentation of data in coherence with study design and PAP.

All data sets, PK parameters and the PK report will be audited by CSC Quality Assurance (QA) for compliance with this Pharmacometric Analysis Plan, as well as internal CSC SOPs. A QA release statement will be provided with the report.

10 ARCHIVING

The project documentation (documents, records, and data) will be retained in hardcopy for a period of three years following project completion at CSC (Montreal, Quebec, Canada). During these retention periods, electronic versions of project documentation will be retained on CSC's servers, with access limited to personnel assigned to the project.

12 LISTINGS, TABLES, AND FIGURES

The following list of tables and figures, and their associated shells, are provided in order to provide a framework for the display of data from this study. The list of tables and figures and their shells may change based on the data collected following completion of the conduct of study.

LIST OF PLANNED IN-TEXT TABLES

Geometric Mean (CV%) Plasma Pharmacokinetic Parameters of Abaloparatide-sMTS Following Single Application of 300 µg Abaloparatide-sMTS –Day 1

Geometric Mean (CV%) Plasma Pharmacokinetic Parameters of Abaloparatide-sMTS Following Multiple Daily Applications of 300 µg Abaloparatide-sMTS - Day 15

Geometric Mean (CV%) Plasma Pharmacokinetic Parameters of Abaloparatide-sMTS Following Multiple Daily Applications of 300 µg Abaloparatide-sMTS - Day 29

Geometric LS Means Ratios and 90% Confidence Intervals of Abaloparatide Following Multiple Daily Applications Versus Single Application of 300 µg Abaloparatide-sMTS – Day 15

Geometric LS Means Ratios and 90% Confidence Intervals of Abaloparatide Following Multiple Daily Applications Versus Single Application of 300 µg Abaloparatide-sMTS – Day 29

LIST OF PLANNED IN-TEXT FIGURES

Mean (+SD) Plasma Concentrations of Abaloparatide-sMTS vs. Time Following Single or Multiple Daily Applications of 300 µg Abaloparatide-sMTS (Linear and Semi-Log Scales)

LIST OF PLANNED PHARMACOKINETIC TABLES AND FIGURES

8. TABLES AND FIGURES

8.1. TABLES

8.1.1. Plasma Abaloparatide-sMTS Concentration-Time Tables

Table 8.1.1.1 Plasma Concentrations of Abaloparatide-sMTS Following Single Application of 300 µg Abaloparatide-sMTS – Day 1

Table 8.1.1.2 Plasma Concentrations of Abaloparatide-sMTS Following Multiple Daily Applications of 300 µg Abaloparatide-sMTS – Day 15

Table 8.1.1.3 Plasma Concentrations of Abaloparatide-sMTS Following Multiple Daily Applications of 300 µg Abaloparatide-sMTS – Day 29

8.1.2. Plasma Abaloparatide-sMTS Pharmacokinetic Parameter Tables

Table 8.1.2.1 Plasma Pharmacokinetic Parameters of Abaloparatide-sMTS Following Single Application of 300 µg Abaloparatide-sMTS – Day 1

Table 8.1.2.2 Plasma Pharmacokinetic Parameters of Abaloparatide-sMTS Following Multiple Daily Applications of 300 µg Abaloparatide-sMTS – Day 15

Table 8.1.2.3 Plasma Pharmacokinetic Parameters of Abaloparatide-sMTS Following Multiple Daily Applications of 300 µg Abaloparatide-sMTS – Day 29

8.1.3. Plasma Abaloparatide-sMTS Terminal Phase Characterization Tables

Table 8.1.3.1 Terminal Phase Characterization of Abaloparatide-sMTS Following Single Application of 300 µg Abaloparatide-sMTS – Day 1

Table 8.1.3.2 Terminal Phase Characterization of Abaloparatide-sMTS Following Multiple Daily Applications of 300 µg Abaloparatide-sMTS – Day 15

Table 8.1.3.3 Terminal Phase Characterization of Abaloparatide-sMTS Following Multiple Daily Applications of 300 µg Abaloparatide-sMTS – Day 29

